10.0 Criteria for Removal from Study

- Progressive disease
- Intercurrent illness that prevents further administration of treatment,
- Patient request,
- Pregnancy or
- General or specific changes in the patient's condition render the patient unacceptable for further treatment in the judgment of the investigator.

11.0 Background Drug Information

11.1 Sorafenib

Chemical Name:

4-{4-[3-(4-chloro-3-trifluoromethyl-phenyl) ureido]-phenoxy}-pyridine-2 carboxylic acid methanamide-4-methylbenzenesulfonate.

Other Names:

BAY 54-9085 is the tosylate salt of SORAFENIB

Classification:

Kinase inhibitor (Raf, VEGF-R, and PDGF-R)

Mechanism of Action:

The ras/raf signaling pathway is an important mediator of responses to growth signals and angiogenic factors. This pathway is often aberrantly activated in human tumors due to presence of activated ras, mutant b-raf, or over expression of growth factor receptors.

SORAFENIB is a potent inhibitor of c-raf, and wild-type and mutant b-raf in vitro. Additionally, further characterization of SORAFENIB revealed that this agent inhibits several receptor tyrosine kinases (RTKs) that are involved in tumor progression (VEGF-R, PDGF-R, Flt3, and c-KIT) and p38 α , a member of the MAPK family.

Molecular Formula:

$C_{12}H_{16}ClF_3N_4O_3 \cdot X \cdot C_7H_8O_3S$

M.W.:

SORAFENIB: 637 Daltons; SORAFENIB (free base): 465 Daltons

Approximate Solubility:

0.19 mg/100 mL in 0.1 N HCl, 453 mg/100 mL in Ethanol, and 2971 mg/100 mL in PEG 400.

How Supplied:

SORAFENIB is supplied as an immediate-release film-coated, round, and salmon color tablet containing 200 mg of the free base, SORAFENIB, and the excipients croscarmellose sodium, microcrystalline cellulose, hydroxypropylmethylcellulose, sodium lauryl sulfate, and magnesium stearate. The film-coat consists of hydroxypropylmethyl cellulose, polyethylene glycol, titanium dioxide and red iron oxide. The film coating has no effect on the rate of release of the active SORAFENIB .

SORAFENIB 200 mg tablets are supplied in bottles of 120 tablets.

Storage:

Store at controlled room temperature (15°C – 25°C). Storage conditions should not exceed 25°C.

Stability:

Stability studies with the 200 mg dosage form are ongoing. The current shelf life is 24 months when stored at controlled room temperature.

Route(s) of Administration:

Orally

Reported Adverse Events and Potential Risks:

Body as a whole:

fatigue, flu-like syndromes, fever, arthralgia

Gastrointestinal:

diarrhea, pancreatitis, elevated amylase/lipase, abdominal pain/cramping, nausea, flatulence, dyspepsia

Hepatic:

increased bilirubin, ALT, AST, GGT, LDH, and alkaline phosphatase

Metabolic and Nutritional:

anorexia

Skin:

hand-foot syndrome, characterized by palmar and plantar erythema; rash/desquamation, hypersensitivity reactions, dry skin, alopecia, nail changes, vitiligo

The following adverse events have been reported on trials but with the relationship to SORAFENIB still undetermined:

arthritis, brain stem stroke, dyspnea, hypertension, increase PT and PTT, and weight loss.

Method of Administration:

Patients will be instructed to take SORAFENIB on an empty stomach (1 hour before or 2 hours after eating).

Potential Drug Interactions:

SORAFENIB is metabolized by the P450 CYP3A enzyme and has been shown in preclinical studies to inhibit multiple CYP isoforms. Therefore, it is possible that SORAFENIB may interact with drugs that are metabolized by the P450 CYP isoenzymes or with drugs that inhibit CYP 3A. Close monitoring is recommended for patients taking agents with narrow therapeutic indices and metabolized by the liver, such as warfarin, phenytoin, quinidine, carbamazepine, phenobarbital, cyclosporine, and digoxin. Additionally, SORAFENIB is 97% to 99% protein bound; however, no drug interactions have been reported in studies, thus far.

Availability

SORAFENIB is commercially available.

Consult the package insert on www.nexavar.com for additional information

11.2 Azacitidine

Chemical Name:

4-amino-1-beta-D-ribofuranosyl-1,3,5-triazin-2(1H)-one

Other Names:

5-azacytidine, azacytidine, 5-AC, 5-AZC

Classification:

DNA methylation inhibitor

Mechanism of Action:

Azacitidine is a pyrimidine nucleoside analog of cytidine. Azacitidine is believed to exert its antineoplastic effects by causing hypomethylation of DNA and direct cytotoxicity on abnormal hematopoietic cells in the bone marrow. Hypomethylation may restore normal function to genes that are critical for differentiation and proliferation.

Molecular Formula:

C₈H₁₂N₄O₅

M.W.:

Azacitidine : 244 Daltons

How Supplied:

Azacitidine is supplied in a sterile form for reconstitution as a suspension for subcutaneous infection or reconstitution as a solution for further dilution for intravenous infusion. Vials of azacitidine contain 100 mg of azacitidine and 100 mg of mannitol as a sterile lyophilized powder.

Storage:

Store un-reconstituted vials at 25° C (77° F); excursions permitted to 15°-30° C (59°-86° F) (See USP Controlled Room Temperature). There is no need to protect azacitidine from exposure to light.

Stability:

Azacitidine reconstituted for subcutaneous administration may be stored for up to 1 hour at 25°C (77°F) or for up to 8 hours between 2°C and 8°C (36°F and 46°F). Azacitidine reconstituted for intravenous administration may be stored at 25°C (77°F), but administration must be completed within 1 hour of reconstitution.

Route(s) of Administration:

Subcutaneous or intravenous

Reported Adverse Events and Potential Risks:

Body as a whole:

weakness, rigors, fever, arthralgia, myalgia,

Gastrointestinal:

diarrhea, constipation, abdominal pain/cramping, nausea, vomiting

Hematologic:

Anemia, thrombocytopenia, neutropenia

Metabolism and Nutrition:

hypokalemia, anorexia

Renal:

Elevated serum creatinine, renal failure, renal tubular acidosis

Skin:

injection site erythema, petechiae, ecchymosis

Other:

hepatic coma, dizziness, headache, shortness of breath

Method of Administration:

See section 6.1 for complete details.

Potential Drug Interactions:

No formal assessments of drug-drug interactions between azacitidine and other agents have been conducted.

Availability

Azacitidine is commercially available.

Consult the package insert on www.vidaza.com for additional information

12.0 Adverse Event Reporting

Refer to **Appendix C** for Leukemia-Specific Adverse Event Recording and Reporting Guidelines. Only unexpected AEs will be recorded in the Case Report Form (CRF).

12.1 Pregnancies:

If a female subject or partner of a male subject becomes pregnant during the study dosing period or within 3 months from the discontinuation of dosing, the investigator should report the information to the MDACC IRB as if it is an SAE. The expected date of delivery or expected date of the end of the pregnancy, last menstruation, estimated fertility date, pregnancy result and neonatal data etc., should be included in this information. The investigator will follow the medical status of the mother, as well as the fetus, as if the pregnancy is an SAE.

When the outcome of the pregnancy falls under the criteria for SAEs [spontaneous abortion, induced abortion, stillbirth, death of newborn, congenital anomaly (including anomaly in a miscarried fetus)], the investigator should respond in accordance with the report procedure for SAEs.

- "Spontaneous abortion" includes abortion and missed abortion.

- Death of an infant within 1 month after birth should be reported as an SAE regardless of its relationship with the study drug.

- If an infant dies more than 1 month after the birth, it should be reported if a relationship between the death and intrauterine exposure to the study drug is judged as "possible" by the investigator.

- In the case of a delivery of a living newborn, the "normality" of the infant is evaluated at the birth.

- "Normality" of the miscarried fetus is evaluated by visual examination unless test results which indicate a congenital anomaly are obtained prior to miscarriage.

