1.0 Objectives

1.1 Primary objectives:

1. To determine the clinical activity (CR +CRi) of the combination of AZA and sorafenib in patients with untreated acute myeloid leukemia and High risk MDS with FLT3-ITD mutation.

1.2 Secondary objectives:

1. To determine the toxicity profile of the combination of AZA and sorafenib in patients with untreated acute myeloid leukemias and MDS with FLT3-ITD mutation.
2. To determine potential mechanisms of synergy with this combination and its correlation with response.

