2.1 Sorafenib

Sorafenib (Nexavar, Bayer-Onyx) is an oral, small molecule kinase inhibitor that was initially developed as a Raf inhibitor. Subsequent laboratory characterization of sorafenib demonstrated that it is a multikinase inhibitor of several other targets including vascular endothelial growth factor receptor-2 (VEGFR-2), VEGFR-3, and platelet-derived growth factor receptor-beta (PDGFR-[beta]). Due to its inhibition of VEGFR, sorafenib has been classified as an antiangiogenic drug. Sorafenib garnered initial attention when its antitumor activity in renal cell cancer was noted in early clinical trials. More recently, on the basis of a phase III trial, sorafenib was approved by the Food and Drug Administration (FDA) for the treatment of metastatic renal cancer and hepatocellular cancer.

Sorafenib was initially identified through a library screen as a small molecule that inhibits C-Raf. In addition to C-Raf, sorafenib is a multikinase inhibitor of several other targets including wild type and mutant B-Raf, VEGFR-2, VEGFR-3, PDGFR-[beta], Flt-3, c-Kit, and fibroblast growth factor receptor-1. In contrast, Erk1, Erk2, insulin-like growth factor, c-met, EGFR, and protein kinase C are not inhibited by sorafenib.¹²

A series of phase I trials involving a range of sorafenib doses (50–800 mg) and schedules (intermittent and continuous) have been conducted. Plasma drug levels of 400 mg twice daily are well tolerated and higher than those necessary to inhibit Raf kinase, as well as VEGFR and PDFGR. Thus the recommended dose for single agent phase II testing is 400 mg twice daily.

In the phase I studies, sorafenib was well tolerated; the rate of grade 3 toxicities was low and no grade 4 toxicities were reported. The most common drug-related side effects were hand-foot syndrome (23%), rash (26%), fatigue (39%), diarrhea (55%), hypertension (35%), stomatitis (7%), neuropathy (22%) and alopecia (16%).

Based on results from preclinical and phase I studies, sorafenib was expected to cause growth arrest and clinical disease stabilization rather than tumor shrinkage. Assessment of cytostatic drugs and disease stabilization in phase II studies is challenging in that it is often difficult to distinguish drug effect versus prolonged natural history of the disease in any single patient. One proposed phase II design for cytostatic agents is the randomized discontinuation trial (RDT).

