ratio of 0.348 (range, 0.009 – 0.934). They had received a median of 2 prior treatments (range, 0 -7) including 13 previously untreated patients. Twenty (35%) patients had received ≥ 3 prior regimens and 12 had failed prior therapy with FLT3 kinase inhibitors (6 with AC220, 2 with PKC412, and 9 with sorafenib, either as monotherapy or with chemotherapy or plerixafor); 4 patients had failed 2 prior FLT3 inhibitors. The overall CR/CRi/PR rate among the 57 patients is 44%, including 16 (28%) with CRi and 8 (14%) with CR and 1 (2%) with PR. The response rate among the previously untreated patients was 62% and among relapsed patients 39%. Patients have received a median of 3 (range, 1 - 27) treatment cycles with the median number of cycles to response among the responders being 2 (range, 1 – 4) and the median time to achieving response, 2.1 months (range, 0.8 – 4.6 months). The median duration of CR/CRi is 2.4 months (range, 0.8 – 24.8 months). Seven patients have proceeded to allogeneic stem cell transplant. The most common study drug-related adverse events were rash and fatigue with no deaths attributable to study medications. One patient developed grade 3 cardiomyopathy. With a median follow-up of 8.6 months (range, 6.1 – 26.9), 13 patients remain alive, 5 still in remission. The median overall survival of the 57 patients was 6.3 months, and 12.4 months in the 25 responding patients. Mean FL levels at cycle 2, day 0 and cycle 2, day 10 were 27 pg/mL and 54 pg/mL, respectively, which is significantly lower than those seen previously in studies of FLT3 kinase inhibitor plus chemotherapy.¹⁸

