13.3 Analysis method

Data analysis will be performed using SAS or S-plus, as appropriate. All patients who received at least 1 dose of the combined agents will be included in the intent-to-treat analysis for efficacy. Demographic and disease characteristics of the patients at registration will be summarized using descriptive statistics such as mean, standard deviation (SD), median and range. Overall response rates will be presented with 95% confidence intervals. The association between response and patient and disease characteristics will be examined by two-sample t-test or Chi-square test.

The data from all patients who received the combined therapy during the study will be included for safety analysis. Subjects who entered the study and did not take any of the study drugs and had this confirmed will not be evaluated for safety. The severity of the toxicities will be graded according to the NCI CTCAE v4.0 whenever possible. We will follow standard reporting guidelines for adverse events. Safety data will be summarized by category, severity and frequency. The proportion of patients with AEs will be estimated, along with the Bayesian 95% credible interval. These descriptive summaries will be provided for all patients for each safety parameter by cycle, grade, and relationship to treatment.

This study will be conducted as described in this protocol, except for an emergency situation in which the protection, safety, and wellbeing of the patient requires immediate intervention, based on the judgment of the investigator or his/her designee. In the event of a significant deviation from the protocol, the investigator will notify the MDACC surveillance committee following the institutional guidelines.

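### Section 12.0 limits the CRF to unexpected AEs, while sections 13.3 and 1.2 need AEs of every kind; unless Appendix C provides otherwise, summaries built from the CRF would understate the drugs' known effects

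*Combined protocol and SAP*

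**What the plan says.** Section 12.0 refers the reader to Appendix C for leukemia-specific recording and reporting guidelines and then states: "Only unexpected AEs will be recorded in the Case Report Form (CRF").

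Section 13.3 describes the safety analysis without that limit. "The proportion of patients with AEs will be estimated, along with the Bayesian 95% credible interval". It adds: "These descriptive summaries will be provided for all patients for each safety parameter by cycle, grade, and relationship to treatment". It names no data source.

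Section 1.2 lists as a secondary objective: "To determine the toxicity profile of the combination of AZA and sorafenib", in the trial population.

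The protocol also describes what is already known of the drugs:

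- Section 2.1 gives single-agent phase I rates for sorafenib: diarrhea 55%, fatigue 39%, rash 26% and hand-foot syndrome 23%.
- The account of the earlier trial of this same combination, at the end of section 2.2, says: "The most common study drug-related adverse events were rash and fatigue".
- Section 11.1 lists the same effects among reported sorafenib events, for example "fatigue, flu-like syndromes, fever, arthralgia" and "hand-foot syndrome, characterized by palmar and plantar erythema; rash/desquamation"; diarrhea is under its gastrointestinal heading.
- Section 11.2 gives a similar list for azacitidine, including the cytopenias.

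**The concern.** The recording rule and the analysis plan do not fit together. An analysis of AEs by grade, cycle and attribution needs a record of AEs in general. The CRF, the only AE form that the available text names, is told to leave out the expected ones.

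The loss would not be random. It would fall on the events that the protocol itself presents as the usual effects of these drugs. An event that is not entered is indistinguishable from an event that did not happen, so the estimate would be low and its interval would look precise. The secondary toxicity objective would then be answered mainly for rare or surprising events.

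**Working it through.** **The passages side by side**

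| Section | Scope of AEs | Source named |
|---|---|---|
| 12.0 | unexpected only | CRF; Appendix C for guidelines |
| 13.3 | AEs, all patients, by cycle, grade and relationship | none |
| 1.2 | toxicity profile of the combination | none |

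Only section 12.0 draws a distinction between expected and unexpected events.

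**Inputs for a worst-case illustration**

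- Number of patients: 52 (section 13.0), all assumed treated.
- Event rates: the section 2.1 single-agent rates. Rates for the combination in this trial may differ.
- Prior: section 13.3 states none, so the Beta(0.6, 1.4) toxicity prior of section 13.2 is borrowed. As a check on that prior, the section 13.2 rule applied to it reproduces all 12 toxicity boundaries of Table 13.1 (4, 5, 7, 9, 10, 12, 13, 15, 16, 18, 19, 20).
- Recording: every listed term is treated as expected at any grade, and the CRF is the only source.

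**Formula.** For x patients with the event out of 52, the posterior is Beta(0.6 + x, 1.4 + 52 − x). The interval runs from its 2.5% to its 97.5% point.

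**Results**

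| Event | Rate × 52 | x | Interval if all recorded | Recorded under this reading |
|---|---|---|---|---|
| Diarrhea | 0.55 × 52 = 28.6 | 29 | 42% to 68% | 0/52, 0% to 5% |
| Fatigue | 0.39 × 52 = 20.3 | 20 | 26% to 51% | 0/52, 0% to 5% |
| Rash | 0.26 × 52 = 13.5 | 14 | 16% to 40% | 0/52, 0% to 5% |
| Hand-foot syndrome | 0.23 × 52 = 12.0 | 12 | 13% to 35% | 0/52, 0% to 5% |

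The choice of prior matters little. With Beta(0.5, 0.5), 0/52 gives 0% to 5% and 29/52 gives 42% to 69%. With Beta(1, 1) they give 0% to 7% and 42% to 68%.

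**Between the extremes.** The documents do not say what share of events would be recorded, so the shares here are assumed. Suppose 21 of 52 patients (40%) have an event:

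- all 21 recorded: 27% to 53%
- 16 recorded: 19% to 44%
- 10 recorded: 10% to 31%, which excludes the 40% that occurred

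**The case against.** The strongest reply is that the governing text has not been seen. Section 12.0 sends the reader to Appendix C before it states the limit. Appendix C may define what counts as unexpected, set rules by grade, or name another AE record. Its absence here is not a fault in the plan. This stands, and it makes the size of the harm conditional. It does not remove the conflict, because the limiting sentence is in the protocol body and needs to agree with both Appendix C and section 13.3.

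A second reply is that section 13.3 never says that it uses the CRF. Other records exist: section 4.2.1 puts the justification for dose reductions in the chart, the hypertension text in section 5 keeps a blood pressure diary with the research chart, and section 14.2 archives source data. This also stands in part. Summaries abstracted from charts would not be limited by the CRF rule. But the available text does not say that the analysis will be done that way.

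A third reply is that 0/52 is the extreme of one reading. That is correct. If grade counts toward expectedness, some severe events of listed terms would be entered, and the section 2.1 rates are for one drug alone.

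A reader might also infer that the toxicity stopping rule in section 13.2 would fail to trigger. The documents do not support this. Section 13.2 does not say where its counts come from, and grade 3 and 4 events have to be identified anyway for the dose actions in section 5. Nor does it follow that section 13.2 counts only treatment-related events. Its opening words mention treatment-related toxicity, but both it and section 13.0 define the monitored event without attribution.

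**Conclusion.** The concern holds as a conflict between a stated recording rule and a stated analysis. Unless Appendix C provides otherwise, AE proportions and summaries built from the section 12.0 CRF would understate the known effects of the two drugs. In the worst case an event in over half the patients would be shown as absent (diarrhea 29/52 against 0/52). That figure rests on the listed-term reading, the CRF as sole source, the single-agent rates and a borrowed prior. The likely size cannot be derived from the documents.

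It would be too strong to say that the section 13.3 summaries cannot be produced at all, or that understatement is certain. Neither section 13.3's source nor Appendix C's content is known from the available text. For section 13.2 only a query remains: what is the count source, and does attribution matter? The point should be fixed, but it does not affect the design figures.

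**What to change.** 1. **Section 12.0.** Replace the limiting sentence with wording such as: *The CRF records all unexpected AEs of any grade, and all non-hematologic AEs of grade 3 or higher whether expected or not, each with grade, attribution and cycle.*
2. **Expected grade 1–2 AEs and expected hematologic AEs.** Step 1 alone does not restore these, and section 2.1 reports few sorafenib events of grade 3 or above. Choose one of two routes. Either record them in short form (worst grade per patient per cycle, with attribution), or state in sections 13.3 and 1.2 that the summaries and the objective cover only what is recorded.
3. **Appendix C.** Reconcile section 12.0 with it. If it sets up another AE source, name that source in section 13.3.
4. **Query for section 13.2.** Ask it to name the source of the Table 13.1 toxicity counts and to say whether attribution matters. This review does not choose between the definitions.

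The cost is a few sentences, matching CRF instructions and modest extra data entry. The second route in step 2 avoids most of the data entry but narrows the toxicity objective. The sample size and the Table 13.1 boundaries do not change.

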13.0 Statistical Considerations

This is a single arm study using the dosage level recommended from a previously conducted and published phase I/II study in patients with relapsed AML. The sample size is 52. The trial will be continuously monitored for efficacy and toxicity (non-hematological \geq grade 3). The method of Thall, Simon, and Estey will be used to perform interim efficacy and safety monitoring.¹⁴

13.1 Efficacy

The primary endpoint is the overall response (CR+CRi) after three cycles of treatment. The historical data suggested the overall response rate is 45%. With the assumption that the improved overall response rate to be 65%, it is estimated that a total of 52 evaluable patients will yield 83% power at a significance level of 5% based on chi-square test. The trial will be continuously monitored. The study will be stopped early if the data suggest that:

$$\Pr(\pi > 0.45 | \text{data}) < 0.05$$

Here π is the overall response (OR) rate. That is, if at any time during the study we determine that there is a less than 5% chance that the average OR rate is greater than 45%, we will terminate the study. The OR rate is assumed to follow a non-informative prior of Beta (0.9, 1.1).

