13.2 Monitoring Of non-hematological \geq grade 3 toxicities

With the concern of treatment related toxicity, the non-hematological toxicity (\geq grade 3) will also be closely monitored during the study.

Denote the probability of toxicity by P_E . We assume $P_E \sim \text{beta}(0.6, 1.4)$. Our stopping rule is given by the following probability statement:

$$\Pr(P_E > 0.3 | \text{data}) > 0.95 .$$

That is, we will stop the trial if, at any time during the study, we determine that there is more than 95% chance that the toxicity is more than 30%.

Patients will be monitored by a cohort size of 4 according to the following stopping boundaries for overall response and toxicity. The design software Multic Lean Desktop (version 2.1) developed by the Department of Biostatistics at M. D. Anderson Cancer Center (MDACC) was used to generate the futility/toxicity stopping boundaries and the OC table.

Table 13.1. Stopping boundaries for overall response and toxicity

Number of patients evaluated	Stop the trial if there are this many responses	Stop the trial if there are this many toxicities
4	0	4
8	0-1	5-8
12	0-2	7-12
16	0-3	9-16
20	0-5	10-20

24	0-6	12-24
28	0-8	13-28
32	0-9	15-32
36	0-11	16-36
40	0-12	18-40
44	0-14	19-44
48	0-15	20-48

Table 13.2. Operating characteristics of futility and safety monitoring

True Toxicity Rate	True overall response Rate	Prob (stop the trial early)	Average sample size
0.2	0.25	0.94	17.2
	0.35	0.59	31.9
	0.45	0.21	43.8
	0.55	0.07	48.8
	0.65	0.03	50.6
0.3	0.25	0.95	16.4
	0.35	0.64	29.7
	0.45	0.32	40.4
	0.55	0.2	44.9
	0.65	0.16	46.5
0.4	0.25	0.97	14.0
	0.35	0.82	23.1
	0.45	0.66	30.1
	0.55	0.61	33.2
	0.65	0.59	34.3
0.5	0.25	1.0	10.9
	0.35	0.97	15.1
	0.45	0.95	18.1
	0.55	0.94	19.5
	0.65	0.93	20

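### Does the 83% power in 13.1 mislead because it leaves out the interim looks and the sidedness of the test?

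*Combined protocol and SAP*

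**What the plan says.** Section 13.1 defines the endpoint: "The primary endpoint is the overall response (CR+CRi) after three cycles of treatment". It sets the reference rate: "The historical data suggested the overall response rate is 45" per cent. It takes 65% as the improved rate and adds that "it is estimated that a total of 52 evaluable patients will yield 83% power at a significance level of 5% based on chi-square test". It then announces continuous monitoring, with a futility rule introduced by "The study will be stopped early if the data suggest that": the trial ends if the posterior probability that the response rate exceeds 0.45 falls below 0.05, under a Beta(0.9, 1.1) prior.

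Section 13.2 adds a safety rule under a Beta(0.6, 1.4) prior. The trial stops if "there is more than 95% chance that the toxicity is more than 30" per cent. On timing it says: "Patients will be monitored by a cohort size of 4 according to the following stopping boundaries for overall response and toxicity". Table 13.1 lists 12 looks, from 4 to 48 patients. Table 13.2 gives the early-stop probability and the average sample size for 20 combinations of true response and toxicity rates, but no probability of a positive result.

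For the final analysis, section 13.3 says: "Overall response rates will be presented with 95% confidence intervals". It names no test against 45%.

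**The concern.** A reader may take 83% as the chance that the trial succeeds when the true response rate is 65%. A trial with 12 opportunities to stop has a lower chance than that, and neither 13.1 nor Table 13.2 prints it. If the shortfall were large, 52 patients might be too few.

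The missing sidedness looks like a second gap. A one-sided 5% test would reject at 30 of 52, a two-sided one at 31. If the plan really left that choice open, a result of 30/52 could be called positive or negative after the data were seen, and a single-arm trial has no control group to settle the matter.

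**Working it through.** **Inputs.** From 13.1: reference rate 0.45, alternative 0.65, n = 52, level 5%, chi-square test, Beta(0.9, 1.1) prior. From 13.2: Beta(0.6, 1.4) prior, limit 0.30, looks every 4 patients, Tables 13.1 and 13.2. From 13.3: 95% interval.

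**1. Reproduce the 83%.** In a single-arm trial the test is one-sample. Two-sided 5%, normal approximation:

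- null SE = √(0.45 × 0.55 / 52) = 0.0690
- alternative SE = √(0.65 × 0.35 / 52) = 0.0661
- power = Φ[(0.20 − 1.96 × 0.0690) / 0.0661] = Φ(0.98) = 83.6%

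The exact power of the implied rule (31 or more of 52) is P(X ≥ 31 | 52, 0.65) = 0.8317, and P(X ≥ 31 | 52, 0.45) = 0.0241. One-sided 5% would give 0.8932 with a cutoff of 30 (error 0.0449). Two arms of 52 or of 26 would give 54% or 30% (two-sided). Of these, only the two-sided one-sample reading gives 83%.

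**2. Does the plan leave the cutoff open?** The one-sample chi-square is (x − 23.4)² / (52 × 0.45 × 0.55) = (x − 23.4)² / 12.87.

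- x = 30: 6.6² / 12.87 = 3.38, below 3.84 (p = 0.066); exact 95% CI 43.2–71.3%, which includes 45%
- x = 31: 7.6² / 12.87 = 4.49, above 3.84 (p = 0.034); exact 95% CI 45.1–73.0%, which excludes 45%

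The Wilson and Wald intervals split at the same place: their lower limits are 44.2% and 44.3% at 30/52, and 46.1% and 46.3% at 31/52. Test, power figure and interval agree on 31.

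**3. Reproduce the monitoring tables.** The two posterior rules return all 12 rows of Table 13.1. At 20 patients, for example, Pr(rate > 0.45) is 0.035 with 5 responses and 0.089 with 6; Pr(toxicity > 0.30) is 0.961 with 10 events and 0.906 with 9. An exact binomial recursion over the 12 looks, with response and toxicity independent, returns all 20 rows of Table 13.2 to within 0.01 (stop probability) and 0.1 (average sample size).

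**4. Put the looks into the power.** At a true 65%:

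- P(pass all futility looks) = 0.9828
- P(pass them and reach 31 or more of 52) = 0.8221, so futility costs 0.8317 − 0.8221 = 0.0096
- P(31 or more, given that 52 are reached) = 0.8221 / 0.9828 = 0.8365

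Under independence, the chance of passing all toxicity looks multiplies 0.8221:

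| True toxicity | P(pass toxicity looks) | P(reach 52 and ≥31) |
|---|---|---|
| 0.20 | 0.985 | 0.810 |
| 0.25 | 0.949 | 0.780 |
| 0.30 | 0.853 | 0.701 |
| 0.40 | 0.419 | 0.345 |

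Of the 0.1305 lost at 30% toxicity (0.8317 − 0.7012), 0.0096 is futility and 0.1209 is safety stopping. The printed tables give nearly the same answer directly: 0.83 × (1 − 0.03) = 0.81 and 0.83 × (1 − 0.16) = 0.70.

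With an association between response and toxicity (odds ratio 0.25 to 4), the result stays at 81% for 20% toxicity and ranges from 69% to 72% for 30%.

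**5. Type I error.** At a true 45%, P(reach 52 and ≥31) is 0.0233 at 20% toxicity and 0.0202 at 30%, both below the fixed-sample 0.0241.

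**The case for a change.** The best case for a change is that a success rule should be written down rather than recovered from a power figure, and that 30% toxicity is the protocol's own limit and a row of its own table, so 70% is a fair scenario to report. The repair would cost one clause and one column.

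Part of this stands. Section 13.1 would read better if it said that the test is two-sided and that the power applies when the trial is not stopped early. But 30/52 is not an open case. Calling it positive needs a one-sided test (exact p = 0.045), which the plan does not name and which does not yield its stated power. At 20% toxicity the chance of ending on exactly 30/52 is 0.8684 − 0.8097 = 0.059 at a true 65%, and 0.0431 − 0.0233 = 0.020 at a true 45%.

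A printed cutoff of 31 would also hold only for a denominator of exactly 52. Sections 4.2.1 and 4.3 require a full first cycle for efficacy evaluation, while 13.3 analyses everyone who received a dose. With 54 or 58 patients the same test needs 32 or 34 responses.

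As to the 70%, a safety stop at a toxicity rate equal to the limit is the rule doing its job. Counting it as lost efficacy power is a convention that 13.1 does not adopt; its sentence is about 52 evaluable patients.

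The uncited 45% is a separate matter. The nearest figure, in section 2.2, is 44% and includes one partial response (CR plus CRi was 24/57, or 42%), in a group of whom 44 of 57 had been treated before. That bears on what the reference rate means, not on whether 83% is right.

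**Conclusion.** The concern does not call for a change. The 83% is correct for what it describes: a two-sided 5% one-sample test on 52 evaluable patients. Futility monitoring takes about 1 point from it, and both rules together take about 2 points at 20% toxicity. The 13-point gap at 30% toxicity is about 1 point of futility and 12 of intended safety stopping, and a reader can derive it from Table 13.2 by one multiplication. The unstated sidedness is missing detail that the named test, the power figure and the planned interval settle in the same way.

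Adding a clause and a column would change neither the sample size, the boundaries, the error rate nor the conclusion drawn from any result. The figures with both rules assume that response and toxicity are independent, which is not stated but does reproduce Table 13.2. The documents predict no toxicity rate, so 81% and 70% are scenarios, not forecasts.
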